## 6 Study Procedures and Observations

### 6.1 Schedule of Procedures and Observations

The study-specific assessments are detailed in this section and outlined in Section 6. Screening assessments must be performed within 28 days prior to the first dose of investigational product. Any results falling outside of the reference ranges may be repeated at the discretion of the investigator. All on-study visit procedures are allowed a **window of  $\pm$  3 days** unless otherwise noted. Treatment or visit delays for public holidays or weather conditions do not constitute a protocol violation.

A written, signed, informed consent form (ICF) and a Health Insurance Portability and Accountability Act (HIPAA) authorization must be obtained before any study-specific assessments are initiated. A copy of the signed ICF will be given to the subject and a

copy will be filed in the medical record. The original will be kept on file with the study records.

All patients who are consented will be registered in OnCore®, the UCSF Helen Diller Family Comprehensive Cancer Center Clinical Trial Management System (CTMS). The system is password protected and meets HIPAA requirements.

## 6.1.1 Pretreatment Period

### 6.1.1.1 Screening Assessments

With the exception of CT or MRI imaging for the purposes of tumor/lesion assessment, all screening procedures and assessments must be completed within 28 days of the Day 1 Visit. Any requisite imaging must be obtained within 42 days of day 1 of study participation.

- Physical examination
- Vital signs
- Complete medical history
- Baseline conditions assessment
- ECOG Performance status
- Ophthalmologic exam including slit lamp examination and visual acuity prior to dilation, and a dilated fundoscopic evaluation and slit lamp examination.
- Neurological evaluation
- Pulse oximetry
- History of prior treatments and any residual toxicity relating to prior treatment
- Baseline medications taken within 28 days of Day 1
- Brief Pain Inventory (BPI) short form
- Laboratory evaluations
  - Complete blood count (CBC) with differential and platelet count and coagulation tests
    - Coagulation indices including international normalized ratio (INR), prothrombin time (PT) and activated partial thromboplastin time (aPTT) do not need to be repeated at screening if patients have already completed a biopsy through the companion radiologically guided mCRPC protocol or they have been deemed ineligible for biopsy.
  - Blood chemistry assessment, including:
    - Alkaline phosphatase, aspartate aminotransferase/alanine aminotransferase (ALT/AST), total bilirubin, calcium, phosphorus, blood urea nitrogen (BUN), creatinine, total protein, albumin, fasting glucose, potassium, sodium, chloride, bicarbonate, uric acid, lactate dehydrogenase (LDH), fasting lipid panel (low-density lipoprotein [LDL], total cholesterol, triglycerides)
  - Prostate Specific Antigen (PSA)
  - Serum total testosterone

- Imaging (CT or MRI) of chest, abdomen and pelvis for tumor/lesion assessment, contrast is to be used unless clinically contraindicated.
- Electrocardiogram (ECG)
- Bone scan (Technetium)
- Prophylactic therapy (initiated 0-3 days prior to first selinexor dose)
- Tumor biopsy -- optional, per companion Radiologically Guided Biopsy protocol of mCRPC, offered to patients treated at UCSF, UCLA, UC Davis, Oregon Health Sciences University, University of British Columbia

## **6.1.2 Treatment Period**

### **6.1.2.1 Study Procedures, Cycle 1, Day 1**

- Physical examination
- Vital signs
- Performance status
- Evaluation of adverse events
- Concomitant medications
- Brief Pain Inventory (BPI) short form
- Laboratory evaluations
  - CBC with differential and platelet count
  - Blood chemistry assessment
  - PSA
  - Selinexor serum levels – obtained 10 minutes prior to first dose, then 2 hours after first dose, and 4 hours after first dose.
  - Treated leukocyte lysate collection– obtained 10 minutes prior to first dose
  - Serum macrophage inhibitory cytokine-1 (MIC-1) – obtained 10 minutes prior to first dose
  - Leukocyte collection for XPO1 inhibition analysis - obtained 10 minutes prior to first dose, then 4 hours after first dose

### **6.1.2.2 Study Procedures, Cycle 1, Day 3 – via telephone**

- Evaluation of adverse events

### **6.1.2.3 Study Procedures, Cycle 1, Day 15**

- Serum macrophage inhibitory cytokine-1 (MIC-1) – obtained 10 minutes prior to first dose
- Leukocyte collection for XPO1 inhibition analysis - obtained 10 minutes prior to first dose, then 4 hours after first dose

### **6.1.2.4 Study Procedures Cycle 2+, Day 1**

These procedures must be completed within 3 days of Day 1

- Physical examination
- Vital signs
- Performance status
- Evaluation of adverse events
- Concomitant medications
- Brief Pain Inventory (BPI) short form
- Imaging (CT or MRI) for tumor/lesion assessment - at completion of cycle 2, cycle 4, cycle 6, day 22-28, and then every 12 three cycles weeks thereafter
- Bone scan (Technetium) - at completion of cycle 2, cycle 4, cycle 6, day 22-28 and every 12 weeks thereafter
- Ophthalmologic exam to be performed every 3 months while on study if cataracts are identified at screening and/or as clinically indicated. This exam will include slit lamp examination and visual acuity prior to dilation, and a dilated fundoscopic evaluation and slit lamp examination. Ophthalmologic evaluations will be performed by the Department of Ophthalmology at the participating study institution.
- Laboratory evaluations
  - CBC with differential and platelet count
  - Blood chemistry assessment
  - PSA - monthly and at time of progression
  - Serum macrophage inhibitory cytokine-1 (MIC-1) – at cycles 2 and 3 – obtained 10 minutes prior to dose
  - Leukocyte collection for XPO1 inhibition analysis – at cycles 2 and 3 - obtained 10 minutes prior to dose, then 4 hours after dose

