**Table 6.1 Schedule of Study Procedures and Assessments**

Visits must occur ±7 days of planned visit unless otherwise noted.

Period/ Procedure	Screening				Cycle 1		Cycle 2 and future Cycles	End of Treatment visit	Follow- up visits
	-28 to 0	1	3 	15	1	1	Within 30 days of last dose	By phone Every 6 months	
Treated leukocyte lysate 		X							
Serum MIC-1 mRNA 		X		X	X				
Selinexor PK 		X							
Testosterone	X								
Imaging procedures									
CT c/a/p with contrast or MRI	X					X 			
ECG/EKG	X								
Bone scan (Technetium)	X					X 			

 Required at screening and as clinically indicated while on study. Coagulation labs include PT, PTT/INR.

 Only offered to patients at UCSF, UCLA, UC Davis, Oregon Health Sciences University, University of British Columbia. If no intervening therapy is initiated, the tumor biopsy can be performed within a 2-month window (60 days) of day 1 of Selinexor.

 Including alkaline phosphatase, ALT/AST, total bilirubin, calcium, phosphorus, (BUN), creatinine, total protein, albumin, fasting glucose, potassium, sodium, chloride, bicarbonate, uric acid, LDH, fasting lipid panel (LDL, total cholesterol, triglycerides).

 Monthly and at time of progression

 Only Cycle 2 and Cycle 4, Day 22-28, and at time of progression

 PK samples will be collected on Cycle 1 Day 1 only. PD Samples will be collected on Cycle 1 Day 1 and 15, Cycle 2 Day 1, and cycle 3 Day 1. Refer to section 6.3 for PK and PD collection schedule.

 At the completion of Cycle 2, Cycle 4, Cycle 6, Day 22-28, and every 12 weeks thereafter

 Required at screening, every 3 months thereafter if cataracts identified at screening and if clinically indicated, and at the end of treatment study visit.

 C1D3 visit will be conducted via telephone call

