## 8.2 Determination of Sample Size and Accrual Rate

### 8.2.1 Sample Size and Power Estimate

In the first stage, 18 patients will be accrued. If there are 10 or fewer patients classified as progression-free at 16 weeks in these 18 patients, the study will be stopped. Otherwise, up to 36 additional patients will be accrued for a maximum total of 54. The null hypothesis is that 55% of patients are progression-free at 16 weeks. The alternative hypothesis is 75% are progression-free at 16 weeks. The null hypothesis will be rejected if 36 or more patients classified as progression-free at 16 weeks are observed in 54 patients. There is a 60.9% chance of stopping early for futility. This design yields a type I error rate of 0.048 and power of 90.0%.

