#### Time to confirmed development of $\geq 2$ new bone lesions

Time to development of  $\geq 2$  new bone lesions, defined as the time interval between the date of treatment initiation and the date of documented new lesions. Bone scans will be performed at week 8, 16, 24, and every 12 weeks thereafter; evaluation criteria is defined by the PSAWG2 criteria for bone scan evaluation. The time will be 'backdated' to when the  $\geq 2$  new lesions were detected if a second scan is done to confirm progression.

Kaplan-Meier methods will be used to estimate the median time to development of  $\geq 2$  new bone scans with a 95% confidence interval.

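### CT/MRI and bone scans are scheduled by completed cycle, but the decision rules need status at week 16 with no assessment window; if cycles slip, late scans can favour the drug.

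*Combined protocol and SAP*

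**What the plan says.** The two decision rules rest on a landmark. In section 8.2.1 the stage 1 rule reads "If there are 10 or fewer patients classified as progression-free at 16 weeks in these 18 patients, the study will be stopped", and the null is rejected if "36 or more patients classified as progression-free at 16 weeks are observed in 54 patients". Section 8.4.2 makes the proportion without radiographic progression at 16 weeks the primary endpoint and times rPFS from treatment initiation. It gives no window around week 16.

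The imaging schedule is written by cycle. Section 6.1.2.4 places the bone scan "at completion of cycle 2, cycle 4, cycle 6, day 22-28 and every 12 weeks thereafter", and its CT/MRI line names the same three cycle-based scans. Table 6.1, footnote 7, covers both modalities: "At the completion of Cycle 2, Cycle 4, Cycle 6, Day 22-28, and every 12 weeks thereafter". Section 8.4.3 uses the calendar instead: "Bone scans will be performed at week 8, 16, 24, and every 12 weeks thereafter". The bone-scan text in section 7.3 likewise calls the first reassessment an 8-week scan.

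Other relevant rules:
- **Holds.** Table 5.3 delays or interrupts dosing for many toxicities. Section 5.2 discontinues the patient only when a drug-related delay exceeds 21 days, with an exception for clinical benefit.
- **Dating.** In section 7.3, bone progression after the first reassessment is dated at the scan. Lesions first seen at the first reassessment and later confirmed are dated back to it.
- **Visit windows.** Section 6.1 allows 3 days either side; the header of Table 6.1 allows 7.

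**The concern.** A cycle-based scan and a calendar landmark coincide only when every cycle starts on time, and the undelayed Cycle 4 slot ends at the landmark with no slack. Suppose a hold pushes the cycle back, the scan moves with it, and the 16-week status is read from the date of progression. Then a patient whose progression is first seen on that scan is counted as progression-free at week 16.

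The direction matters more than the exact size. Holds are caused by toxicity, so poorer tolerability would raise the apparent success rate. In a single-arm trial no control group shares the shift. At stake are the futility stop and the error rate of the final test. At the stage 1 boundary, 10 against 11 of 18, one patient's classification can decide whether the trial continues.

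**Working it through.** **1. The plan's own figures.** Inputs from section 8.2.1: 18 patients in stage 1, stop at 10 or fewer; 54 in total, reject at 36 or more; null rate 0.55, alternative 0.75. With X1 ~ Bin(18, p) and X2 ~ Bin(36, p):

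- P(early stop) = P(X1 ≤ 10)
- P(reject) = sum over x = 11 to 18 of P(X1 = x) × P(X2 ≥ 36 − x)

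At p = 0.55, early stop is 0.6085 and rejection 0.0477. At p = 0.75, rejection is 0.9007. The stated 60.9%, 0.048 and 90.0% all reproduce; the design itself is not in question.

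**2. Where the Cycle 4 scan falls.** With 28-day cycles, Cycle 4 Day k is study day 84 + k + shift, and elapsed weeks = (study day − 1)/7.

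| Net cycle shift | Day 22-28 slot | Elapsed weeks | With ±3 days | With ±7 days |
|---|---|---|---|---|
| 0 days | 106-112 | 15.0-15.9 | 103-115 | 99-119 |
| 7 days | 113-119 | 16.0-16.9 | 110-122 | 106-126 |
| 14 days | 120-126 | 17.0-17.9 | 117-129 | 113-133 |
| 21 days | 127-133 | 18.0-18.9 | 124-136 | 120-140 |

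After a one-week shift only the first day of the nominal slot is exactly week 16; the rest lies beyond it. If the visit windows apply to imaging, they can put either an undelayed scan or one shifted by a week on either side of the landmark.

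**3. Illustrative effect on the error rates.** These inputs are assumptions, because the documents give none of them: a share f of patients has a shifted scan; event times are exponential with 55% event-free at 16 weeks; status is judged by progression date. A shifted patient is then judged on the Cycle 2 scan alone, at week w between 8 and 11.

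- Weekly hazard = −ln(0.55)/16 = 0.0374
- Event-free at week 8: 0.742; at week 11: 0.663
- Share whose progression is hidden: g = 0.742 − 0.55 = 0.192, down to g = 0.663 − 0.55 = 0.113
- Apparent null rate = 0.55 + f × g if all events are scan-detected, or 0.55 + f × g/2 if half are

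For example, f = 0.20 and g = 0.192 give 0.55 + 0.038 = 0.588. Putting these rates into the step 1 formulas gives:

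| Shifted | Type I error, all events on scans | Early stop, all events on scans | Type I error, half on scans |
|---|---|---|---|
| 0% | 0.048 | 0.61 | 0.048 |
| 10% | 0.066-0.082 | 0.54-0.57 | 0.056-0.063 |
| 20% | 0.090-0.132 | 0.48-0.53 | 0.066-0.082 |

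**The case against.** The strongest reply is that the bias needs several unstated readings at once.

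- **Bone scans already have calendar weeks in 8.4.3.** True. For bone scans this is an internal conflict to reconcile, and only CT/MRI timing rests on cycles alone. The procedures section and the schedule table, from which sites work, are still cycle-based for both. A reader might infer that time to new bone lesions is also lengthened, but 8.4.3, which defines that endpoint, uses the calendar schedule.
- **No text says a hold moves the cycle.** True. Section 1.4 repeats cycles every 28 days, and some Table 5.3 actions skip doses or reduce frequency within the cycle. If held doses are simply omitted, the scan stays on day 106-112. Equally, nothing keeps scans on the calendar when a cycle is delayed.
- **Visit windows can pull a scan back.** True, so a one-week shift does not necessarily carry the scan past week 16. Nothing directs sites to the early side, though, and two different windows are stated.
- **Status may be meant as the result of the nominal week-16 scan.** Under that reading a delayed scan still counts and the bias disappears. The plan does not say which reading applies.
- **Not every event depends on scans.** Sections 2.4.1 and 8.4.2 also count death and prostate-cancer surgery or radiation, and each lists a clinical event. Confirmed bone lesions first seen at the first reassessment are dated back to it. Both points reduce the effect, hence the half-on-scans column.

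**Conclusion.** The point holds as an unresolved conflict with a possible one-sided consequence. The imaging schedules in 6.1.2.4 and Table 6.1 match 8.4.3 and the 16-week landmark only if no cycle slips, and the plan does not define how the 16-week status is taken. If a hold shifts the cycle and status is date-based, the error favours the drug.

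A reader might infer that any one-week dosing delay moves the deciding scan past the landmark, or that the type I error is in fact inflated by a known amount. The documents support neither. They do not say that holds shift cycles, the windows work in both directions, and no delay rate is given. On the stated assumptions, with 10-20% of patients shifted, type I error would be about 0.066-0.132 if all events are scan-detected and about 0.056-0.082 if half are, against 0.048. These figures are illustrative. The sample size and decision boundaries are sound as computed.

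**What to change.** - **Section 6.1.2.4 and Table 6.1, footnote 7:** schedule CT/MRI and bone scans at weeks 8, 16 and 24 and every 12 weeks thereafter, counted from Cycle 1 Day 1 regardless of dose holds, matching 8.4.3.
- **Section 6.1 and Table 6.1:** state one visit window for imaging in place of the two now given.
- **Section 8.4.2:** take the 16-week status from the scheduled week-16 scan within a fixed window, for example day 106-119, and count progression first seen on that scan as progression by week 16. Classify patients whose scan is missing or outside the window by a stated rule, for example as not progression-free unless a later scan shows no progression.

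This needs wording changes only. There are no extra scans, and the sample size, boundaries and dosing rules stay as they are. The small cost is that in delayed patients the scan no longer coincides with a cycle visit.

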### 6.1.3 End-of-Treatment Study Procedures

- To be completed within 30 days of the last dose of study drug.
- Physical examination
- Vital signs
- Performance Status
- Evaluation of adverse events
- Concomitant medications
- Brief Pain Inventory (BPI) short form
- Tumor biopsy -- optional, per companion Radiologically Guided Biopsy protocol of mCRPC, offered to patients treated at UCSF, UCLA, UC Davis, Oregon Health Sciences University, University of British Columbia
- Ophthalmologic exam including slit lamp examination and visual acuity prior to dilation, and a dilated fundoscopic evaluation and slit lamp examination.
- Laboratory evaluations
  - CBC with differential and platelet count
  - Blood chemistry assessment
  - PSA

#### **6.1.4 End-of-treatment long-term follow-up**

- To be completed at 6 month intervals after the last dose of study drug.
- Telephone visit for assessment of adverse events, concomitant medications and subsequent antitumor therapy.

#### **6.1.5 Discontinuation of Therapy**

The Investigator will withdraw a patient whenever continued participation is no longer in the patient's best interests. Reasons for withdrawing a patient include, but are not limited to, disease progression, the occurrence of an adverse event or a concurrent illness, a patient's request to end participation, a patient's non-compliance or simply significant uncertainty on the part of the Investigator that continued participation is prudent. There may also be administrative reasons to terminate participation, such as concern about a patient's compliance with the prescribed treatment regimen.

**Table 6.1 Schedule of Study Procedures and Assessments**

Visits must occur ±7 days of planned visit unless otherwise noted.

Period/ Procedure	Screening	Cycle 1			Cycle 2 and future Cycles	End of Treatment visit	Follow- up visits
		1	3 	15			
Study Day/Visit Day	-28 to 0	1	3 	15	1	Within 30 days of last dose	By phone Every 6 months
Informed consent	X						
Baseline conditions	X						
AE assessment		X	X		X	X	X
Concomitant medications		X			X	X	X
Treatment/Drug Administration							
Selinexor		Oral, twice weekly (On Days 1 and 3 of each week 1-3 of each 4 week cycle)					
Clinical procedures							
Physical exam	X	X			X	X	
Vital signs	X	X			X	X	
Medical history	X						
Disease assessment	X				X		
Performance status	X	X			X	X	
Neurologic evaluation 	X						
Ophthalmic evaluation	X 				X 	X 	
Pulse oximetry 	X						
BPI Short Form	X	X			X	X	
Tumor biopsy(optional)	X 					X 	
Laboratory procedures							
CBC w/ Diff & platelets	X	X			X	X	
Coagulation 	X						
Blood chemistry 	X	X			X	X	
PSA	X				X 	X	
Leukocyte collection for XPO1 inhibition 		X		X	X		

**Table 6.1 Schedule of Study Procedures and Assessments**

Visits must occur ±7 days of planned visit unless otherwise noted.

Period/ Procedure	Screening				Cycle 1		Cycle 2 and future Cycles	End of Treatment visit	Follow- up visits
	-28 to 0	1	3 	15	1	1	Within 30 days of last dose	By phone Every 6 months	
Treated leukocyte lysate 		X							
Serum MIC-1 mRNA 		X		X	X				
Selinexor PK 		X							
Testosterone	X								
Imaging procedures									
CT c/a/p with contrast or MRI	X					X 			
ECG/EKG	X								
Bone scan (Technetium)	X					X 			

 Required at screening and as clinically indicated while on study. Coagulation labs include PT, PTT/INR.

 Only offered to patients at UCSF, UCLA, UC Davis, Oregon Health Sciences University, University of British Columbia. If no intervening therapy is initiated, the tumor biopsy can be performed within a 2-month window (60 days) of day 1 of Selinexor.

 Including alkaline phosphatase, ALT/AST, total bilirubin, calcium, phosphorus, (BUN), creatinine, total protein, albumin, fasting glucose, potassium, sodium, chloride, bicarbonate, uric acid, LDH, fasting lipid panel (LDL, total cholesterol, triglycerides).

 Monthly and at time of progression

 Only Cycle 2 and Cycle 4, Day 22-28, and at time of progression

 PK samples will be collected on Cycle 1 Day 1 only. PD Samples will be collected on Cycle 1 Day 1 and 15, Cycle 2 Day 1, and cycle 3 Day 1. Refer to section 6.3 for PK and PD collection schedule.

 At the completion of Cycle 2, Cycle 4, Cycle 6, Day 22-28, and every 12 weeks thereafter

 Required at screening, every 3 months thereafter if cataracts identified at screening and if clinically indicated, and at the end of treatment study visit.

 C1D3 visit will be conducted via telephone call

## 6.2 PK and PD Calendar

TIME POINT	Total Volume of blood (ml)	PK	PDn		
		Plasma (1 tube x 1ml)	Cytokines (1 tube x 1ml)	Leukocytes (2 PAX gene tubes x 2.5ml)	Leukocytes (1 tube x 3ml)
Cycle 1, Day 1					
Pre-dose (within 10 min before administration)	13	X	X	X	X
2 hr (~10 min) post dose	2	X			
4 hr (~20 min) post dose	7	X		X	
Cycle 1, Day 15					
Pre-dose (within 10 min before administration)	7		X	X	
4 hr (~20 min) post dose	5			X	
Cycle 2 and 3, Day 1					
Pre-dose (within 10 min before administration)	7		X	X	
4 hr (~20 min) post dose	5			X	

## 6.3 Dietary Restrictions

Patients should be encouraged to always take selinexor within 30 minutes before or after a meal, so as to prevent variations in plasma KPT-330 exposure related to prandial state. There are no specific restrictions on meal size nor content.

Patients will be instructed to avoid alcohol consumption within 4 hours of selinexor administration, given concern for glutathione depletion and subsequent impaired clearance of selinexor (see section 6.3).

## 6.4 Prohibited Medications

The primary metabolism of selinexor *in vitro* and *in vivo* appears to be inactivation by glutathione (GSH) conjugation. This process can be mediated in the absence of proteins, indicating that it is thermodynamically favorable. *In vitro* studies using human liver microsomes confirm *in vivo* findings that selinexor undergoes minimal CYP450 metabolism. There was also no induction of CYP450 activity observed for CYP1A2 or CYP3A4.

Therefore, administration of selinexor with drugs which undergo substantial GSH conjugation should be minimized until further data are available. These drugs include acetaminophen (paracetamol) and alcohol (ethanol). Alcohol ingestion should be avoided 4 hours before and after selinexor administration in order to minimize GSH depletion. In the event that GSH depletion is believed to be contributing to patients' symptoms, signs or laboratory findings, replenishment with S-adenosylmethionine (SAM) oral (e.g., 400 mg PO BID-TID) or N-acetylcysteine (e.g., up to 140 mg/kg PO loading dose followed by 70 mg/kg PO Q4 hours thereafter) until symptoms resolve. It should be noted that no studies of selinexor in combination with acetaminophen have been performed to date and that these recommendations are empirical.

Androgenic-anabolic steroids including exogenous testosterone or synthetic testosterone derivatives (e.g., oxandrolone) are contraindicated in patients with metastatic castration resistant prostate cancer, and therefore must not be administered at any point during trial participation.

Complete and updated information is available in the Investigational Drug Brochure.

